## **8.0 RESPONSIBILITIES OF THE INVESTIGATOR**

### **8.1 Adherence to the Study Protocol**

The Investigator must ensure adherence to the procedures outlined in this Study Protocol. The procedures set out in this study protocol, pertaining to the conduct, evaluation, and documentation of this study, are designed to ensure that the Investigator abides by GCP as described in the ICH Guidelines Topic E6: “Guideline for Good Clinical Practice.” Compliance with these regulations also constitutes compliance with the ethical principles described in the current revision of the Declaration of Helsinki. The study will also be carried out in keeping with local legal and regulatory requirements.

### **8.2 Data Handling and Record Keeping**

The Investigator must ensure that proper source documentation for all study activities are diligently maintained and securely kept. The Investigator will transfer all relevant data to the Case Report Form as stipulated in this Study Protocol and his/her signature on the Case Report Form guarantees completeness and integrity of these data. The Investigator will store all study related supplies in a secure and locked location. In addition, the Investigator will ensure that all Case Report Forms will be maintained for a period of two years after the conclusion of the study.

## **9.0 REGULATORY OBLIGATIONS**

### **9.1 Institutional Review Board**

The study protocol, informed consent forms (all versions), and any specific advertising will be submitted to and approved by Independent Investigational Review Board before the start of the study. A form must be signed by the chairman or designee of the IRB noting the approvals. This notification will be provided to SkinMedica for notification of study initiation.

**9.2 Protocol**

The Investigator signing the protocol signature page will act as the Principal Investigator at this site. Protocols will be noted as approved by the Investigator by placement of his signature on the Investigator's Signature Page. Copies of the IRB approved protocol and informed consents will be provided to SkinMedica.

**9.3 Informed Consent**

An Informed Consent Form (ICF) that includes all of the relevant elements currently required by FDA or state regulations will be provided to each prospective study subject at screening and before enrollment into the study. The type and method of study, any potential or possible hazards, and the subject's right to withdraw from the study at any time will be explained to the subjects by the Investigator or Designee. Once the Investigator or Designee is assured that an individual candidate understands the implications of participating in this study, the subject will be asked to give consent by signing and dating in the appropriate areas of the Informed Consent Form. The Investigator or Designee will also sign and date the ICF. A copy of the IRB approved ICF will be given to the subject for the subject's records and the original will be filed in the subject's binder or folder.

**9.4 Protocol and Informed Consent Changes**

Changes to the protocol or Informed Consent Forms will be implemented as amendments to the original document and approved by the IRB. The approvals will be processed in accordance with the established IRB procedures. Copies of all protocol and ICF amendments/revisions, along with letters noting IRB approval, will be submitted to SkinMedica, as this may affect safety. Any addenda, amendment or revision that substantially alters the study design or increases potential risk to the subject will require the subject's consent to continue in the study.

**9.5 Study Monitoring**

The site will be responsible for internal verification of complete and accurate data collection and confirming adherence to the protocol throughout the study. The study may be monitored by Sponsor representatives to ensure that the protocol and GCP guidelines are being followed and to assist in resolving any difficulties encountered while the study is in progress. The monitoring may include site visits and frequent communications (telephone, fax, email, letters).

## **10.0 CONFIDENTIALITY OF RECORDS**

Information about the subject's health taken during this study may be used and given to others by the study coordinators, the medical staff, the respective study center and by the subject's doctors and their other healthcare providers. The subject's doctors and their healthcare providers may share health information about the subject with the investigator and study coordinator. The study coordinator and the providers may share that information with researchers participating in this study's laboratories conducting tests for this study. A final study report may be shared with SkinMedica, Inc.; The U.S. Food and Drug Administration (FDA); Department of Health and Human Services (DHHS) agencies; other U.S. and foreign government agencies that watch over quality, safety and effectiveness of research.

All research related personnel will ensure subject confidentiality is maintained. All subject related documents will be identified by subject initials and subject identification numbers. All subject related documents will be filed in individual subject binders or folders and stored in confidence by the site only to be accessed by research related personnel.

## **11.0 DELEGATION OF INVESTIGATOR RESPONSIBILITIES**

The Investigator should ensure that all persons assisting with the trial are adequately informed about the protocol, any amendments to the protocol, the study treatments, and their trial-related duties and functions. The investigator should maintain a list of sub-investigators and other appropriately qualified persons to whom he has delegated significant trial-related duties.

## **12.0 DIRECT ACCESS TO SOURCE DATA/DOCUMENTS**

The Investigator must ensure that institutional regulations, the Informed Consent Form, and the HIPAA Authorization clearly permit study-related monitoring, audits, IRB review, and regulatory inspections providing direct access to source data and documents.

## **13.0 ADVERSE EVENTS AND REPORTING**

### **13.1 Serious And/Or Adverse Event Reporting**

A serious adverse event is any untoward medical occurrence, that, at any dose:

- results in death;
- is life-threatening;

- requires in-subject hospitalization or prolongation of existing hospitalization;
- results in persistent or significant disability/incapacity;
- is a congenital anomaly/birth defect; or
- is an important medical event.

Throughout the study, subjects will be monitored for signs and symptoms of adverse events. An adverse event is any pathological or unintended change in the structure, function or chemistry of the body that occurs during the study, irrespective of causality, including any illness, injury, toxicity, sensitivity, or sudden death. The condition must either not be present pre-study or must worsen in either intensity or frequency during the study.

An unanticipated adverse study drug event is any drug-related adverse event, which is not identified in nature, severity, or frequency in current literature on the test article.

All adverse events, including serious and study drug related or unanticipated adverse drug events, must be recorded and assessed by the Investigator. In the event of an adverse event, serious adverse event or unanticipated adverse drug event, the physician will provide optimal subject care.

Subjects who have had a serious adverse event must be followed clinically until all parameters, including laboratory values, have either returned to normal or are otherwise explained.

Any serious adverse event or unanticipated adverse drug event occurring in this study will be analyzed and identified by the investigator and reported to the IRB within 10 business days, as per IND regulations and FDA Guidance. The investigator will also determine the event related to the study drug and report that event to the manufacture of the device, if necessary.

Serious adverse events will be reported to the Sponsor within 24 hours (or the next working day). The main Sponsor contact for serious adverse events is:

[REDACTED]

If death was the outcome of the event on the initial SAE Report, a Follow-up/Final Report, including autopsy report, when performed, must be completed.

### **13.2 Pregnancy During The Study**

If a subject of childbearing potential becomes pregnant at any time while participating during the study, the pregnancy will be deemed an Adverse Event and the subject will stop all protocol related procedures. The investigator will follow-up with the subject until the pregnancy reaches term or until the pregnancy has been resolved.

The Investigator will report the Adverse Event of pregnancy to the IRB within 24 hours of awareness of the event and follow-up reports will be filed with the IRB as information with changes of the pregnancy becomes available.

### **13.3 Anticipated Reactions**

All test materials have the potential to cause some minor side-effects or other reactions. Possible reactions to the test material(s) may include (but are not limited to) subjective sensations (such as itching, burning, stinging, tingling), scaling/dryness, and redness. Additionally, test material(s) applied to the eye areas have the potential to cause eye watering/tearing, redness of the eyes, corneal erosions, and foreign body sensation in the eyes.

Symptoms of mild to moderate irritation, including the examples discussed above, will not be treated as adverse reactions if they are mild in nature. These conditions may or may not resolve over time. Symptoms that are persistent and moderate to severe in nature, or that involve elevation (e.g. edema, papules, vesicles, spreading) will be considered AEs.

In rare cases, it is possible for a subject to develop allergic reactions to the test material(s). This risk is increased for individuals with a history of allergies, and individuals with asthma and/or a history of hives may also be affected. Subjects will be instructed to notify the clinic immediately if they experience an allergic reaction including rash, hives, and itching.

The Investigator or designee will have the final authorization to determine if a reaction will be considered an AE.

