**STUDY SYNOPSIS**

Protocol Number	SKM16-LYT-MEL Amendment 1
Protocol Title	Randomized, Double-blinded, Split-face Study comparing the Cosmetic Efficacy and Tolerability of Two Topical Products in Subjects with Moderate Facial Melasma
Study Duration	3 months (12 Weeks)
Study Population	20 healthy subjects with Fitzpatrick Skin Types III-VI
Objectives	To evaluate and compare the efficacy and tolerability of two topical products in the improvement of facial melasma
Study Design	Single site, investigator-initiated, double-blinded, parallel arm, randomized treatment, split-face, 12-week study comparing the efficacy and tolerability of SkinMedica's cosmetic topical brightener versus generic hydroquinone 4% topical prescription cream. A total of 20 healthy subjects will be enrolled into this study. Subjects will be screened and randomized at Baseline and will return for visits at Weeks 4, 8 and 12. The test products will be applied only to the affected areas (dark patches) twice a day, morning and evening, every day for 12 weeks. Ancillary products will be provided for basic daily skincare regimen use.
Study Products	
 
• SkinMedica Facial Cleanser
 
• SkinMedica Rejuvenative Moisturizer
 
• SkinMedica Essential Defense Mineral Shield Broad Spectrum SPF 35 Sunscreen
 
• Test Product A (Lytera 2.0)
 
• Test Product B (4% Hydroquinone Topical Cream)
 

Eligibility Criteria	Subjects aged 18+ [REDACTED] with symmetrical moderate facial melasma.

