**6.2 Investigator's Tolerability Assessment**

Tolerability of the test products will be assessed through the capture of adverse events reported throughout the study period. Any adverse event(s) experienced by the subject

during the study period, whether related to the treatment or not, will be recorded in the “Case Report Form.”

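### Mild irritation is kept out of adverse reactions in 13.3, but tolerability in 6.2 rests on adverse event capture, so a side difference in mild irritation would probably go uncounted

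*Combined protocol and SAP*

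**What the plan says.** References are to Amendment 1; the original protocol has the same wording in 6.2, 13.1, 13.3 and 13.5.

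- **Objective (Study Synopsis):** "To evaluate and compare the efficacy and tolerability of two topical products in the improvement of facial melasma".
- **Measure (6.2):** "Tolerability of the test products will be assessed through the capture of adverse events reported throughout the study period". No graded irritation scale appears in the readable part of Section 6.
- **AE definition (13.1):** "An adverse event is any pathological or unintended change in the structure, function or chemistry of the body that occurs during the study". This applies whatever the cause, and sensitivity is named among the examples. The only further condition is that the event be new or worsened. On recording: "All adverse events, including serious and study drug related or unanticipated adverse drug events, must be recorded and assessed by the Investigator".
- **Anticipated reactions (13.3):** after listing itching, burning, stinging, tingling, scaling or dryness, and redness, the section says "Symptoms of mild to moderate irritation, including the examples discussed above, will not be treated as adverse reactions if they are mild in nature". It then sets a threshold: "Symptoms that are persistent and moderate to severe in nature, or that involve elevation (e.g. edema, papules, vesicles, spreading) will be considered AEs". It closes with "The Investigator or designee will have the final authorization to determine if a reaction will be considered an AE".
- **Unblinding (13.5):** an AE or serious AE leads to the Investigator or Sub-Investigator becoming unblinded. Under 6.1 the Investigator also grades the half-face MASI.

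**The concern.** Sections 13.1 and 13.3 give different answers for the same event. New mild stinging on one side is an unintended change and a sensitivity under 13.1, so it is an AE to be recorded. Under 13.3 it is not treated as an adverse reaction. Section 6.2 contradicts neither, but 13.3 narrows the only tolerability measure that the readable text names.

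This matters more in a split-face trial than it would in a parallel-group one. Both products are used by the same person, so a systemic event cannot be assigned to a product. The informative tolerability data are local reactions by side, and 13.3 itself presents these symptoms as the expected ones. If the mild ones are dropped, a real difference could be reported as none and read as equal tolerability.

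There are two further weaknesses in 13.3. It uses one term, adverse reactions, for the exclusion and another, AEs, for the threshold, without saying whether they mean the same. It also does not clearly place transient moderate or severe irritation without elevation.

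**Working it through.** The plan gives no reaction rate, alpha, power or tolerability analysis, so there is no planned figure to reproduce. The check is first a comparison of the texts, then a sizing.

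**Texts side by side**

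| Event on one side | 13.1 | 13.3 |
|---|---|---|
| New mild stinging, burning or redness | AE, to be recorded | Not treated as an adverse reaction |
| Transient moderate or severe irritation, no elevation | AE, to be recorded | Not clearly placed; Investigator or designee decides |
| Persistent moderate-to-severe irritation | AE, to be recorded | AE |
| Any reaction with elevation | AE, to be recorded | AE |

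The first row is the conflict. If 13.3 governs, those events do not reach the measure in 6.2.

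**Worst case, no rate assumed.** Input: 20 subjects (Synopsis), hence 20 sides per product. Mild reactions on 20/20 versus 0/20 sides give AE counts of 0 versus 0, unless discretion is used. For a recorded 0/20, the exact two-sided 95% upper limit is 1 − 0.025^(1/20) = 0.168, or 16.8%. It applies only to reactions counted as AEs and bounds nothing about mild irritation.

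**What a test could show with 20 pairs.** For the exact paired (McNemar) test with all *k* discordant pairs one way, p = 2 × 0.5^k:

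- k = 5: 2 × 0.5^5 = 0.0625
- k = 6: 2 × 0.5^6 = 0.031

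At least 6 discordant pairs, all in one direction, are needed at the two-sided 5% level.

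**Illustration with assumed rates.** Suppose 30% of sides react with one product and 10% with the other: 20 × 0.3 = 6 and 20 × 0.1 = 2 affected sides under full recording. One compatible table is: both sides 1, first side only 5, second side only 1, neither 13.

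- Difference: 6/20 − 2/20 = 0.20.
- Wilson 95% limits: 0.145 to 0.519 for 6/20, and 0.028 to 0.301 for 2/20.
- Newcombe paired score interval with continuity-corrected phi: 1 × 13 − 5 × 1 = 8, which is below n/2 = 10, so phi is set to 0.
  - Lower: 0.20 − √[(0.300 − 0.145)² + (0.301 − 0.100)²] = −0.054.
  - Upper: 0.20 + √[(0.519 − 0.300)² + (0.100 − 0.028)²] = 0.431.
- Exact McNemar with 5 versus 1 discordant: p = 2 × (1 + 6)/2^6 = 0.219.

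**Effect of not counting mild reactions.** Expected counted sides = 20 × p × (1 − m), where p is the reaction rate and m is the fraction that is mild and uncounted. Both are assumed, with the same m on each side.

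| m | p = 0.30 | p = 0.10 |
|---|---|---|
| 0 | 6.0 | 2.0 |
| 0.2 | 4.8 | 1.6 |
| 0.4 | 3.6 | 1.2 |
| 0.6 | 2.4 | 0.8 |
| 0.8 | 1.2 | 0.4 |

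With most reactions mild, little is left to compare.

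**The case against.** The strongest objection is that the consequence depends on text that cannot be read. The readable document goes from 4.4 to 6.0, and the questionnaire items and appendices are withheld. A graded, side-specific record may already exist. This stands, and it is why the conclusion is limited to the readable text and the fix is conditional. It does not remove the conflict between 13.1 and 13.3, both of which are readable.

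A second objection is that 13.3 is a specific rule qualifying a general one, or that adverse reactions differs from AEs, so mild irritation remains an AE under 13.1. Either reading is possible. However, 13.1 contains no cross-reference, the terms are not distinguished, and the sentence after the exclusion sets a threshold for AEs, which makes the narrower reading the more natural one.

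Third, the Investigator or designee may class any reaction as an AE. That is a rule for deciding, and the 0 versus 0 case requires that it never be used for mild reactions. It gives no criterion, though, so it does not ensure consistent counting.

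Fourth, other sources exist: the left-and-right questionnaire at Weeks 4, 8 and 12 (6.4), photographs at all visits (6.5), and the subject's agreement to report reactions (3.1). Photographs might show redness or scaling present at a visit, but not stinging, burning, itching or tingling. None of these is named as a tolerability measure.

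Finally, the rates are assumed, and even full recording gives an interval spanning zero in the illustration. That is correct. What is lost is mainly description, not a decisive test.

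**Conclusion.** The concern holds. Section 13.3 conflicts with 13.1 on mild irritation and narrows the one tolerability measure in 6.2, so a between-side difference in mild irritation would probably not enter a comparison that is a stated objective. At the extreme, 20/20 versus 0/20 would be reported as 0 versus 0.

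This rests on three assumptions: 13.3 is applied as its wording most naturally reads, discretion is not used to class mild reactions as AEs, and no unreadable section supplies a side-specific record. Confidence is therefore moderate. More serious local reactions are still captured, so this should be fixed but does not undermine the trial as a whole.

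**What to change.** 1. **Section 6.2:** record every local reaction, mild ones included, by facial side, severity grade, onset and duration. Do this at the Week 4, 8 and 12 visits and when reported between visits, whether or not the reaction is classed as an AE. If an unreadable section already provides this record, name it in 6.2 as the tolerability measure.
2. **Analysis:** summarise the two sides within subject as paired counts and grades with intervals, without relying mainly on a test.
3. **Sections 13.1 and 13.3:** reconcile them under one defined term so that each reaction falls in one class, including transient moderate or severe irritation without elevation. Which class is for the sponsor and investigator to settle.
4. **Section 13.5:** reconcile it in the same edit, so that logging a mild reaction does not unblind the Investigator who grades efficacy.

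The cost should be about one further case report form page, completed at existing visits, and a few lines of text; it needs no extra visits. There are two downsides. The tolerability profile will look less clean. And if mild reactions become AEs without the change to 13.5, the efficacy grader will be unblinded for more subjects, so items 3 and 4 must be made together.

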### **13.4 Unknown/Unforeseeable Risks**

In addition to the risks listed above, there may be some unknown or infrequent and unforeseeable risks associated with the use of the assigned study products. Subjects will be informed both verbally and in writing in a timely manner of any new information, findings or changes to the way the research will be performed that might influence their willingness to continue their participation in this study.

**Pregnancy/Fetal Risks:** The effects of SkinMedica Facial Cleanser, Rejuvenative Moisturizer, Essential Defense Mineral Shield Broad Spectrum SPF 35, Test Product A (Lytera 2.0) and Test Product B (4% Hydroquinone) have not been studied in pregnancy and therefore may be hazardous.

If a subject thinks that she may be pregnant or have become pregnant during the study she is to inform the study doctor immediately. If a subject becomes pregnant or thinks they may be pregnant, they will be removed from the study and the study doctor will refer the subject to seek obstetric care and may request to track their pregnancy and will report to the IRB.

### **13.5 Unblinding**

In the event that a subject experiences an Adverse Event or Serious Adverse Event, the Investigator and/or Sub-Investigator will become unblinded.

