#### **Melasma Severity Rating Scale:**

At the screening/baseline visit and the end of treatment visit (week 12), the Investigator will assess the subject's facial skin for the severity of symmetrical facial melasma using the following Melasma Severity Rating Scale on the left and right facial sides. Subjects must present with a score of 2 for the left and the right facial sides to be enrolled into the study.

Score	Hyperpigmentation Status
0	Cleared: color of melasma lesions approximately equivalent to surrounding normal skin or with minimal residual hyperpigmentation
1	Mild: color slightly darker than the surrounding normal skin
2	Moderate: color moderately darker than the surrounding normal skin
3	Severe: color markedly darker than the surrounding normal skin

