**Overall Hyperpigmentation Scale:**

At all visits (baseline, weeks 4, 8 and 12), the Investigator will globally assess the subject's left and right facial sides for overall hyperpigmentation using the following ten point scale (0 – 9):

None (Score of 0)	Skin is normal in color with no evidence of hyperpigmentation
Mild (Score of 1, 2 or 3)	Several brown spots with increased pigmentation; they are small in size and slightly darker than surrounding skin
Moderate (Score of 4, 5 or 6)	Many brown spots with increased pigmentation; they are medium in size and much darker than surrounding skin
Severe (Score of 7, 8 or 9)	Many large brown spots with increased pigmentation; they are large in size and markedly darker than surrounding skin

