**Half-face Evaluation of Melasma Area Severity Index (MASI) Score**

At all visits, (baseline, weeks 4, 8 and 12), the Investigator will assign a grade for the left and right facial sides, for each of the below units, for the variable A (percentage of each area involved), D (darkness of pigment) and P (pattern of involvement), as described in detail below.

Calculations will be conducted by the sponsor upon receipt of the completed CRFs.

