**Investigator's Global Improvement Assessment- Overall Hyperpigmentation:**

The expert grader will also score an Investigator's Global Improvement Assessment for Overall Hyperpigmentation on the left and right facial sides at all follow-up visits (weeks 4, 8, and 12).

- 0=No change or worsening
- 1=Mild improvement (~25% overall improvement)
- 2=Moderate improvement (~50% overall improvement)
- 3=Marked improvement (~75% overall improvement)
- 4=Complete clearing/Dramatic improvement (~95%+ overall improvement)

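### Any adverse event automatically unblinds the Investigator and/or Sub-Investigator, and the visible text does not keep the efficacy grader blind

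*Combined protocol and SAP*

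**What the plan says.** All references are to the Amendment 1 protocol; Section 13.5 of the original protocol contains the same sentence.

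- **Rule (Section 13.5).** "In the event that a subject experiences an Adverse Event or Serious Adverse Event, the Investigator and/or Sub-Investigator will become unblinded". This one unredacted sentence is the whole section.
- **Trigger (Section 13.1).** An adverse event is any qualifying change during the study, "irrespective of causality, including any illness, injury, toxicity, sensitivity, or sudden death".
- **Limit on the trigger (Section 13.3).** Irritation symptoms "will not be treated as adverse reactions if they are mild in nature". The decision on reactions is discretionary: "The Investigator or designee will have the final authorization to determine if a reaction will be considered an AE".
- **Who grades (Section 6.1).** Melasma Severity Rating Scale: "At the screening/baseline visit and the end of treatment visit (week 12), the Investigator will assess". Overall Hyperpigmentation Scale: the Investigator, at all visits, rates the "left and right facial sides for overall hyperpigmentation using the following ten point scale". Half-face MASI: "the Investigator will assign a grade for the left and right facial sides", also at all visits. Global improvement: "The expert grader will also score an" assessment, with no visible statement of who that grader is or whether that person stays blind.
- **Blinding and allocation.** The Synopsis describes a double-blinded, split-face study in 20 subjects at one site. Section 4.4 assigns one product to each facial side and has unblinded staff randomize and hand out products. Redacted text follows.
- **Analysis (Section 7.0).** It says which subjects are analysed and nothing about grades given after a code break.

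**The concern.** The wording is mandatory and the trigger does not depend on whether anyone needs the assignment. A cold or a sprained ankle meets the adverse event definition, yet knowing which cream is on which cheek would rarely matter to its treatment.

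The cost falls on the efficacy data. The clinical scales are judgements of left against right. Once the grader knows one side's product, the other side's is known too, so the subject's whole treatment contrast is open to expectation. With 20 subjects, each one is 5% of the data (1/20). Subjects with an adverse event need not be a random subset either: product-related reactions may occur more often on one product's side.

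The exposure is partial. Grades made before the event are unaffected, and Mexameter readings and subject questionnaires are not Investigator gradings.

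**Working it through.** **Reading the text**

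1. *Is the trigger conditional?* Section 13.5 sets no condition. Section 13.1 removes causality as a filter. Section 13.3 removes only mild irritation, at the discretion of the Investigator or designee. The product-related trigger is therefore narrower than all skin reactions, but unrelated illness and injury remain.
2. *Can the rule reach the grader?* The Investigator is named both in Section 13.5 and as grader of three by-side scales in Section 6.1. Unblinding only the Sub-Investigator would satisfy the rule, so it permits, but does not require, an unblinded grader.
3. *Does other visible text prevent this?* The double-blinded label and the unblinded-staff line in Section 4.4 do not cover grading after an event. Section 7.0 gives no handling rule.

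**Scale (illustrative)**

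There is no stated figure to reproduce: the visible documents give no adverse event rate, grading SD, test or alpha. From the documents, n = 20 subjects. Assumed: share p of subjects with at least one event; grading shift b, in SD units of the side difference; two-sided 5% paired t-test.

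Expected subjects with an event = 20p. P(at least one) = 1 − (1 − p)^20.

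| p | Expected | P(at least one) |
|---|---|---|
| 5% | 1 | 0.64 |
| 10% | 2 | 0.878 |
| 20% | 4 | 0.988 |
| 30% | 6 | 0.999 |
| 40% | 8 | >0.999 |

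The mean side difference is biased by p × b; for example, 0.3 × 0.5 = 0.15 SD.

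The false-positive rate was simulated with 200,000 replicates: 20 side differences drawn from N(0,1), each subject shifted by b with probability p. Repeat runs agree within about 0.2 percentage points.

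*(a) Every event precedes the analysed grading, the grader is always the person unblinded, and all shifts favour the same product:*

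| b | p = 10% | 20% | 30% | 40% |
|---|---|---|---|---|
| 0.25 SD | 5.1% | 5.5% | 6.1% | 7.0% |
| 0.5 SD | 5.4% | 7.0% | 9.4% | 13.1% |
| 1 SD | 6.6% | 12.2% | 21.0% | 32.9% |

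At p = 5% the same case gives 5.1%, 5.2% and 5.5% for the three shifts.

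*(b) Only half of those subjects are affected (late event, or only the Sub-Investigator unblinded), probability p/2:* across p = 10–40%, about 5.0–5.5% (0.25 SD), 5.1–7.0% (0.5 SD) and 5.4–12.1% (1 SD).

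*(c) Random direction of shift:* 4.9–5.1% throughout.

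**The case against.** - **Redaction.** The strongest reply is that the safeguard may be blacked out. Text after the unblinded-staff line in Section 4.4 is redacted, no Section 5 is visible, and the appendices are redacted. A rule on blinded assessment could sit in any of these. This stands as a limit: the absence of grader protection is a statement about the visible text only. It does not rescue Section 13.5, which is fully visible and would still have to be reconciled with any such rule.
- **Who is unblinded.** The and/or wording, and a separately titled expert grader, mean that harm is possible but not shown. That is correct. Nothing visible requires the protective reading, though, and the other three scales belong to the Investigator by name.
- **Which events matter.** A subject who leaves after an event has no later grades to bias; pregnancy, for instance, ends participation. This reduces the affected share in the same way as case (b).
- **Magnitude.** Every simulation input is assumed, and the plan states no test to which a false-positive rate could apply. This also stands. The criticism rests on the rule itself; the figures only show a range.
- **Photographs.** Standardized photographs at all visits could support a masked re-read of affected grades. That is a reasonable option, but it would need an additional reader and the visible text does not plan it.

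**Conclusion.** The concern holds. Followed as written, Section 13.5 can remove blinding from a double-blinded trial with no care need behind it, and it can do so for the person who grades three of the clinical scales.

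The likely effect is modest. Under the same-direction assumption at 10–40% event incidence, shifts of 0.25 to 0.5 SD raise an assumed 5% error rate to between 5.1% and about 13% if all subjects with an event are affected, and to at most 7.0% if half are. The 33% figure needs the extreme corner: 40% incidence, a 1 SD shift, a single direction, and every event before grading with the grader always unblinded. Random shifts leave the rate at about 5%.

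This should be fixed because the flaw is plain in the text and cheap to remove. Confidence is medium because of the redactions.

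**What to change.** Replace Section 13.5 with text such as:

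> The code stays with the unblinded study staff or the sponsor. It is broken for a subject only when the treating physician judges that knowing the side assignment is needed for that subject's care. Where this can be avoided, the person who grades efficacy is not given the code. The date, reason and recipient of each code break are recorded.

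This leaves the care decision with the treating physician and changes no treatment rule.

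In Section 7.0, keep all subjects in the main analysis and add one sensitivity analysis that leaves out grades made after the grader was unblinded. State its drawback: it removes data in a way that depends on adverse events. Do not require a change of grader within a subject, since that would add between-rater error.

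If redacted text already protects the grader, reconcile it with Section 13.5.

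Cost: one paragraph in an amendment, a code-break log and one extra analysis. It uses the unblinded staff already named in Section 4.4 and needs no additional subjects or visits.
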